Social isolation was recognized as a major threat to the health of older adults long before the Covid-19 pandemic, with as many as one third reporting being isolated and feeling lonely.^{54,54} As the pandemic is predicted to persist throughout 2020, there is growing concern that long periods of COVID-19 related isolation will foster negative physical and mental health outcomes and speed the progression of physical frailty.⁵⁵ Building upon our preliminary findings (described below) and evidence from a large body of established literature on social isolation, we characterized (Table 1) some of the most important risks being faced by our older Veterans and explored opportunities to use remote interventions to reduce obesity and restore their physical function despite their need to isolate.⁵⁶ The proposed research takes the next step by exploring the feasibility, acceptability, and effectiveness of our remote intervention in Veterans who are at especially high risk of further functional decline due to isolation. In our preliminary surveys, we identified "high risk characteristics" that may lead to greater social isolation. Using the same target population in the parent trial, we will specifically recruit and enroll Veterans

Table 1. Risks Imposed by Age- and COVID-19-Related Social Isolation¹

Loss or Lack of:	Aging-related Isolation	Pandemic-related Isolation
Social Interaction	✓	✓
Financial resources, income	✓	✓
Access to medical care	✓	✓
Access to food, cooked meals	+/-	✓
Opportunity to exercise safely	✓	✓
Fulfilling relationships	✓	+/-

¹The +/- symbol indicates that this may or may not be true, depending on circumstances/resources.

meeting these age and COVID-19 related social isolation risk factors in addition to the parent trial inclusion criteria. As explained in the Aims section, the feasibility and acceptability of the intervention for this cohort will be determined, as will the successful attributes and time demands of the specialized attention they will require from interventionists. Pilot data on the effectiveness of the Protein treatment relative to the Control for restoring physical function in this population will also be acquired.

Specific aims:

Aim 1: To evaluate the feasibility (recruitment and retention) and acceptability (participant satisfaction) of a virtual diet and exercise obesity intervention in Veterans at higher risk for negative physical and mental health outcomes during COVID-19 isolation.

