Selection of Subjects:

From the parent study, 42 participants will have 2 or more age and/or COVID-19 related social isolation risk factors (Table 2). These individuals will be randomized into the Parent study's WL-Protein arm (n=21) or the WL-Control arm (n=21)

Table 2. High-Risk Criteria Due to COVID-related Isolation (≥ 2)

Criteria	Definition
Isolated living environment	Lives alone or eats all meals alone
Risk of sarcopenia	Score of ≥ 4 on SARC-F screener
Poor access to medical care	$\leq 10\%$ Service connection
Sensory impairment	Hearing and/or visual impairments that impacts IADLs and/or ADLs
Caregiver burden	Caregiver for grandchildren, children, and/or spouse
Chronic pain	Moderate, severe, or very severe response to SF-36 pain question

Randomization: The following variables will be blocked in this order: 1) Race (white versus black, 2) chronic health conditions (≥ 3 versus <3), and 3) physical function, SPPB score (≥ 8 versus <8). An equal number of participants will be randomized across the two arms to end up with N=42.

Arm 1: High Risk Weight Loss Protein (HR-WL-Protein; n = 21 completers) 10% WL diet with 1.4g protein/kg body wt/day; ≥ 30 g high quality protein per meal

Arm 2: High Risk Weight Loss Control (HR-WL-Control; n = 21 completers) 10% WL diet with 0.8g protein/kg body wt/day

Screening (Two-step process):

Screening Visit Level 1: Confirm 2 or more high risk criteria (see Table 2), confirm $\text{BMI} \geq 30 \text{ kg/m}^2$, confirm SPPB score of 4-11, confirm fasting plasma glucose ≥ 95 and $< 126 \text{ mg/dL}$, confirm Mini-Cog ≥ 3 (or ability to complete all ADL's).

Screening Visit Level 2: Routine blood and urine chemistries and confirm age-normal renal status.

Aim 1:

Feasibility: Recruitment, retention, and intervention resources (defined in detail below)

Acceptability (6 months): participant satisfaction of intervention (defined in detail below)

Aim 2:

Physical Performance (0, 3, 6 months): Short Physical Performance Battery (SPPB) including three domains Balance (side-by-side, semi-tandem, tandem), gait speed (4-meter timed walk), and lower extremity strength (chair stands)

Anthropometrics: Body weights and body composition using Bod-pod.

Insulin Resistance: Glycated Hemoglobin (HbA1c), assessed in whole blood.

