Cognition Testing: (all virtual) CANTAB battery of tests--reaction time, paired associates learning, spatial working memory, pattern recognition memory, delayed matching to sample, and rapid visual information. Other tests are the Symbol Digit Modalities Test of global cognitive ability, the Hopkins Verbal Learning Test of verbal learning, recall, and recognition and the Trail Making Test (TMT) of psychomotor speed and executive function in which participants connect dots according to either number (part A) or alternating number/letter (part B) will be administered virtually as a timed, 2-part, test.

Aim 3:

Muscle Quality (0,3,6 months): the ratio of knee extensor peak torque (Nm) assessed using isokinetic dynamometer to thigh muscle area (cm^2) assessed by using computed tomography

Measurement/Procedure	Time Points ²	Method
Diet/Intervention		
Body weight	Weekly	Same scale, light clothing and no shoes, measured to nearest 0.1 kg

² Participants enrolled after 10/1/2023 will complete a shortened study period of 3 months. Their data will be collected at month 0 and month 3, as outlined in this table. Body weights will still be collected weekly and the Nutrition and Exit questionnaires will be conducted at 3 months.

3-day diet record; Daily food journal (Adherence)	0, 3, 6, months	3-day diet record by multiple pass; analyzed Food Processor (Version 10.13, 2013; ESHA Research); Daily food journal assessed by RD
Protein checklist	Monthly	RedCap analysis
Actigraph, Axis accelerometer (activity counts, step counts, physical activity intensity)	0, 3, 6 months; 7 days each time point	Actigraph WGT3X-BT activity counts at 1-s epoch from three orthogonal axes at 30 Hz sampling frequency. We have been using Actigraphs in previous studies and therefore have not included in the budget.
Nutrition Questionnaires	0,	Food Security Questionnaire
Nutrition Questionnaires	0, 6 months	Nutrition Literacy Questionnaire
Intervention Evaluation	6 months	Exit Questionnaire
Tissue, metabolic analyses		
Routine chemistries, blood	0, 3, 6 months	Metabolic Panel (LabCorp)
Function, body composition		
SPPB (6, 64, 66)	0, 3, 6 months	Balance (side-by-side, semi-tandem, tandem), gait speed (4-meter timed walk), strength (chair stands).
Virtual SPPB	0, 3, 6 months	Balance (side-by-side, semi-tandem, tandem), gait speed (4-meter timed walk), strength (chair stands). All assessments administered virtually.

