The PI will meet at least weekly with study personnel to discuss participants' reactions to outcome measures and assessments, weekly telephone calls, and any adverse events or unanticipated problems. Monthly meetings between the investigators and the project coordinator will allow for ongoing progress reports, including the number of participants currently involved in the study and scheduled data collection from participants, as well as notification and review of any AEs. Safety monitoring for adverse events (AEs) will be conducted in real time by the PI and/or project coordinator. The following information about adverse events will be collected: 1) the onset and resolution of the AE, 2) an assessment of the severity or intensity (use existing grading scales whenever possible), 3) an assessment of the relationship of the event to the study (definitely, probably, possibly or not related), and 4) action taken (e.g., none, referral to physician, start or increase concomitant medication). The PI will determine the severity of the event, will assign attribution to the event, and will monitor the event until its resolution. All adverse events will be reported per Durham VAMC requirements. All Serious, Unanticipated and Related adverse events will be reported to IRB within 5 business days of hearing of the event. All other adverse events will be reported at continuing review.

Withdrawal of Participants

If a participant decides to withdraw from the study, they will be instructed to contact the PI and discuss the reason for withdrawal. This information will be documented to help better understand the reasons that the participant was unable to complete the study.

Data Analysis and Statistical Considerations

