Power Estimate: The sample size of $n = 84$ per group is based directly on our findings in the MEASUR-UP study, which used the same diet treatments, study population, and primary outcome as in the present Aim 1. In MEASUR-UP, the SPPB score for WL-Pro changed by +2.4 units over the course of the study, while the WL-Control group experienced an increase of +0.9 units. The pooled standard deviation of these changes is 1.7. Thus, the MEASUR-UP study observed a standardized difference of $0.88 = (2.4 - 0.9)/1.7$. Differences of this magnitude have been labeled as 'large' in the power analysis literature. Assuming equivalent effect sizes observed in the MEASUR-UP study, an overall sample size of 100 (evenly divided between groups), and a Type-I error rate of 0.05 (two tailed), the power of our design is greater than 99% to declare significance for the effect size observed in the pilot. At 80% power, this design is powered to detect a difference in change scores in the SPPB of 0.96, or a standardized difference of 0.57.

Analysis Plan for the supplemental protocol:

Aim 1: Feasibility-Recruitment capability: Proportion of participants recruited will be calculated as the number of participants deemed potentially eligible and contacted for enrollment divided by the total number of

participants enrolled. Feasibility of recruitment hypothesis: ≥35% of participants approached for recruitment will agree to participate

Feasibility-Retention: Retention proportion retention will be computed by dividing the number of retained subjects at the end of the intervention by the total number randomized into the study.

Retention hypothesis: ≥80% of participants will remain in the study for the duration of the trial

We will calculate the rate of retention and its respective confidence intervals overall and by group. While non-powerful, we will assess if these rates differ by chi-square test of proportion and Poisson regression respectively. In a series of sensitivity tests, we will assess if retention overall was impacted by demographic and high risk variables.

Feasibility-Intervention Tools: Records of intervention tools and time spent to administer them will be used for post-study analysis of intervention tool effectiveness.

Acceptability-Satisfaction: participant satisfaction of intervention delivery, overall experience, and outcomes will be assessed using a Likert scale and open-ended questions.

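### Supplement Aim 1: satisfaction is scheduled only at the end of the intervention, with no score collected from men who leave early, so the acceptability result is likely to be biased upward

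*Combined protocol and SAP*

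**What the plan says.** The supplement's Specific aims state Aim 1 as "To evaluate the feasibility (recruitment and retention) and acceptability (participant satisfaction) of a virtual diet and exercise obesity intervention". Feasibility and acceptability are named side by side, and acceptability is equated with participant satisfaction.

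The list of Aim 1 measures, after the supplement's screening steps, reads "Acceptability (6 months): participant satisfaction of intervention (defined in detail below". The detail it points to is one sentence in the Analysis Plan for the supplemental protocol: "participant satisfaction of intervention delivery, overall experience, and outcomes will be assessed using a Likert scale and open-ended questions". That sentence does not say who answers, how the answers are summarised, or what happens when there is no answer.

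In the supplement's measurement table, the Intervention Evaluation row has one instrument, the "Exit Questionnaire", at 6 months. The table's footnote on men enrolled after 10/1/2023 says: "Body weights will still be collected weekly and the Nutrition and Exit questionnaires will be conducted at 3 months". For those men, 3 months is the end of the study. The life-satisfaction scale in the same table, at 0, 3 and 6 months, does not rate the intervention.

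For men who leave, the section Withdrawal of Participants says: "If a participant decides to withdraw from the study, they will be instructed to contact the PI and discuss the reason for withdrawal". The reason is then documented. That section does not mention the Exit Questionnaire, and the analysis plan does not connect the documented reasons to acceptability.

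**The concern.** When satisfaction is measured only at the end visit, having a score depends on staying, and staying may depend on satisfaction. A man who found the remote programme unworkable is more likely to have left and so to have no score.

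This matters here because the supplement recruits men for isolation, sensory impairment, caregiver burden or chronic pain. Its Table 3 names technology difficulty, sensory impairment and caregiving as barriers to taking part. Men who leave for those reasons hold much of the information Aim 1 seeks. A high score from those who stayed could be read as acceptability in the whole high-risk group.

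**Working it through.** **Inputs from the documents**
- Parent trial (Setting): 112 completers, 30% dropout, approximately 160 enrolled.
- Supplement retention hypothesis (Analysis Plan for the supplemental protocol): at least 80%, with all randomised men as denominator.
- Supplement size (Selection of Subjects): 42 men, 21 per arm. One sentence reads as 42 randomised; the arm labels say 21 completers each. Both readings are carried below.

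**Inputs not in the documents (assumptions)**
- Proportion satisfied among completers: 90%, with 80% as a second case.
- Proportion satisfied among leavers: varied over the full range, 0% to 100%.
- Every man who reaches the end visit answers, and no leaver does.

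**Step 1. The plan's own dropout figure.** 112 / (1 − 0.30) = 160, which matches. The documents give no figure for acceptability itself.

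**Step 2. Men without a score.**
- If 42 are randomised: 0.20 × 42 = 8.4 (about 8), or 0.30 × 42 = 12.6 (about 13).
- If 42 complete: 42 / 0.80 = 52.5, so 53 randomised and 11 without a score; or 42 / 0.70 = 60 randomised and 18 without a score.

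The share is about 20% or 30% on either reading.

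**Step 3. Bias of a rate taken from completers only.** Let r be retention, c the proportion satisfied among completers and v the proportion satisfied among leavers.
- Rate among all randomised = r·c + (1 − r)·v
- Bias = c − [r·c + (1 − r)·v] = (1 − r)·(c − v)

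With c = 90%:

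| Leavers satisfied (v) | All randomised, r = 0.80 | Bias (points) | All randomised, r = 0.70 | Bias (points) |
|---|---|---|---|---|
| 0% | 72% | +18 | 63% | +27 |
| 50% | 82% | +8 | 78% | +12 |
| 90% | 90% | 0 | 90% | 0 |
| 100% | 92% | −2 | 93% | −3 |

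For example, with r = 0.80 and v = 50%: 0.80 × 0.90 + 0.20 × 0.50 = 0.82.

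With c = 80%, the range for all randomised men is 64% to 84% at r = 0.80 (bias +16 to −4) and 56% to 86% at r = 0.70 (bias +24 to −6).

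**Step 4. The same on a Likert mean.** The formula carries over. If leavers score one point lower on average, the completers' mean is too high by 0.20 × 1 = 0.2 points, or 0.30 × 1 = 0.3 points.

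**The case against.** A reader might infer that men who quit are never asked anything. The documents do not support that: the withdrawal section has them discuss their reason with the PI, and it is recorded. What remains is that this contact depends on the man making it, yields a reason rather than a satisfaction score, and is not tied to the acceptability analysis.

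A reader might also take it as established that satisfaction will be overstated. The documents contain no data on how leavers feel. In an older, impaired population, men may leave because of illness or caregiving while content with the programme. If leavers are as satisfied as completers the bias is zero, and if more satisfied it is slightly negative. Upward bias is the likely direction, not a demonstrated one.

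A third tempting step is to say that a comparison of satisfaction between the diets would be biased. No such comparison is planned. The by-group estimates and the chi-square test in the supplement's analysis plan concern retention. The plan also states no satisfied/not-satisfied proportion, so the percentages in the working illustrate one possible summary.

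The best defence is retention. It is reported in the same aim over all randomised men, with confidence intervals and sensitivity tests by demographic and high-risk variables, so large losses would be visible beside the satisfaction score. This reduces the risk of a misleading report. It does not replace the missing scores, because retention shows how many left, not whether they found the programme unacceptable.

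On importance, acceptability has no hypothesis or threshold, unlike recruitment and retention, and the supplement is a feasibility study. That supports treating the point as minor.

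**Conclusion.** The point holds as a minor improvement to the supplement. Followed as written, the plan yields satisfaction scores only from men who reach the end visit, for one of the two parts of Aim 1, and has no rule for the scores that are absent.

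The likely effect is upward bias of 0.20 to 0.30 times the completer–leaver gap. In the 90% illustration, a gap of 40 points gives 8 to 12 points. The extreme cases run from +27 to −3 points across the two retention levels. These sizes rest on assumed satisfaction rates; only the dropout shares come from the documents. The 0.30 figure is the parent trial's enrolment allowance, used as a less favourable case and not as a forecast for the supplement.

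The point does not extend to the parent trial, which has no acceptability aim.

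**What to change.** In the supplement's Aim 1 measures list and the Intervention Evaluation row of its table, time the Exit Questionnaire at the end of the intervention or at withdrawal, whichever comes first. Offer it by phone or online, and have study staff contact men who stop attending instead of waiting for them to call.

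In the Analysis Plan for the supplemental protocol, add three items to the acceptability sentence:
- the number answering out of all men randomised;
- best- and worst-case bounds for those who do not answer, with the Likert summary they are calculated on stated in advance;
- the documented withdrawal reasons, reported alongside satisfaction.

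The worst case counts men who left for health or family reasons as dissatisfied, so it should be labelled a bound and not an estimate. The reporting items need no new data collection and can also cover men who have already finished or left.

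The cost is schedule wording, one short existing form per withdrawal and some staff calls. Some leavers will decline, and the reported satisfaction may be lower.

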Secondary outcomes: muscle quality (the ratio of knee extensor peak torque to thigh muscle area (cm²) assessed by using compute tomography (CT) (in Nm/cm²); insulin sensitivity, Air Displacement Plethysmograph (BodPod) to measure body weight, lean mass, and body fat; waist circumference, function tests (handgrip, 8-ft up and go, 30-sec chair stand, 6-min walk); physical activity (Actigraph); recent falls and fear of falling, diet adherence and nutritional adequacy; activities of daily living and independent activities of daily living; and quality of life and mood indicators (SF-36 Health Status questionnaire, Profile of Mood States questionnaire, and Pittsburgh Sleep Quality Index).

Measurement/Procedure	Time Points ¹	Method
Diet/Intervention		
Body weight	Weekly	Same scale, light clothing and no shoes, measured to nearest 0.1 kg
3-day diet record; Daily food journal (Adherence)	0, 3, 6 months	3-day diet record by multiple pass; analyzed Food Processor (Version 10.13, 2013; ESHA Research); Daily food journal assessed by RD
Protein checklist	Monthly	RedCap analysis
Actigraph, Axis accelerometer (activity counts, step counts, physical activity intensity)	0, 3, 6 months; 7	Actigraph WGT3X-BT activity counts at 1-s epoch from three orthogonal axes at 30 Hz sampling frequency. We

¹ Participants who are consented after 10/1/2023 will participate in a shortened version of the study. Data will be collected at month 0 and month 3 as outlined in this table. Body weights will still be collected weekly and the Nutrition and Exit questionnaires will be conducted at 3 months.

	days each time point	have been using Actigraphs in previous studies and therefore have not included in the budget.
Nutrition Questionnaires	0 months	Food Security Questionnaire
Nutrition Questionnaires	0, 6 months	Nutrition Literacy Questionnaire
Intervention Evaluation	6 months	Exit Questionnaire
Tissue, metabolic analyses		
Routine chemistries, blood	0, 3, 6 months	Metabolic Panel (LabCorp)
Function, body composition		
SPPB (6, 64, 66)	0, 3, 6 months	Balance (side-by-side, semi-tandem, tandem), gait speed (4-meter timed walk), strength (chair stands).
6-minute walk test (aerobic endurance)	0, 3, 6 months	As many walking laps as possible in six minutes between cones placed 40 meters apart
8-ft Up and Go: (agility/dynamic balance)	0, 3, 6 months	Begins seated. On word 'go' stands, walks around a cone 8 feet away, returns to seated.

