Aim 2: To determine the effect size for subsequent studies of virtual interventions for high risk obese older Veterans with physical function as the outcome of primary interest (virtual SPPB). Outcomes will also be collected for the secondary measures of weight loss, physical function, insulin resistance (Glycated Hemoglobin; Hb A1c), cognitive function, and quality of life.

Exploratory Aim 3 (given restoration of full in-person clinical research testing visits):

To determine the effect size for subsequent studies of virtual interventions for high risk obese older Veterans with regards to the primary outcome of (in-person) SPPB and the in-person secondary outcomes of insulin sensitivity and muscle quality (thigh CT scan, knee extensor peak torque).

Achievement of this Aim would allow comparison of the high-risk participants to the participants that do not have 2 or more age and/or COVID-19 related social isolation risk factors (Table 2).

Significance with regard to COVID-19 impact on Veterans:

The COVID-19 pandemic and resulting social isolation is worsening health conditions in all older adults, including Veterans. Obesity is promoted by overeating due to increased stress and/or reduced access to healthy food options. In our recent recruitments for obesity trials, many of our participants are reporting experiencing a marked weight gain since the pandemic came to our community. Deterioration of physical fitness and function are also being documented.⁵⁷ In addition to exacerbating chronic conditions like type 2 diabetes and hypertension, obesity increases the risk of serious complications and death if a COVID-19 infection occurs. There is a critical and time-dependent need to develop strategies to reverse the trend towards obesity-related physical frailty in our vulnerable older Veterans. The proposed research can be initiated quickly because effective remote interventions have already been developed in the parent trial and are ready for use in this study. Another significant point is that the trial also enrolls a substantial proportion of African American Veterans, an important advantage because minority older adults are known to be more vulnerable to COVID-19 complications.⁵⁸

[figure not shown]
Study Design: High risk, obese, male Veterans with prediabetes and SPPB score of 4-11 (out of 12), aged ≥ 55 yrs will be randomized to a higher protein, calorie-restricted diet OR a calorie-restricted diet with RDA level protein in a 6-month trial (Fig. 2).

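### Supplement Aim 2 reports HbA1c, a measure of average glycaemia, as insulin resistance; secondarily, no insulin-based measure is named for insulin sensitivity

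*Combined protocol and SAP*

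**What the plan says.** **Supplement.** Aim 2, under the supplement's Specific aims, names five secondary measures: weight loss, physical function, "insulin resistance (Glycated Hemoglobin; Hb A1c), cognitive function, and quality of life". The list of measures by aim that follows the supplement's screening steps repeats the definition: "Insulin Resistance: Glycated Hemoglobin (HbA1c), assessed in whole blood". The next aim is headed "Exploratory Aim 3 (given restoration of full in-person clinical research testing visits"). Besides in-person SPPB, it covers "the in-person secondary outcomes of insulin sensitivity and muscle quality (thigh CT scan, knee extensor peak torque"). Under Aim 3, the same list of measures has a single entry: "Muscle Quality (0,3,6 months): the ratio of knee extensor peak torque (Nm) assessed using isokinetic dynamometer to thigh muscle area".

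**Parent protocol.** Under Measures and Data Collection Points, the secondary outcomes begin with muscle quality, defined as a ratio with units, and continue with "insulin sensitivity, Air Displacement Plethysmograph (BodPod) to measure body weight, lean mass, and body fat". Insulin sensitivity has no assay, index or unit there. Both schedules have one blood row, routine chemistries at 0, 3 and 6 months, with the method given as "Metabolic Panel (LabCorp"). For later enrollees the parent table's footnote says: "Data will be collected at month 0 and month 3 as outlined in this table".

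**Data lists.** The Privacy, Confidentiality, and Information Security section names routine chemistries, HbA1c, GFR and fasting glucose. It says that plasma for these is taken at all time points.

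**The concern.** The supplement gives a measurement the name of a different construct. HbA1c summarises average glycaemia; insulin resistance concerns the action of insulin. The two can move differently, particularly here, where oral glucose-lowering drugs are allowed if stable (Exclusion Criteria).

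The label matters because supplement Aim 2 exists to supply effect sizes for later studies of virtual interventions. A later team that took the insulin-resistance effect size from this supplement would be using a glycaemia effect size. The distinction also carries scientific weight. Background and Significance cites a trial suggesting that higher protein may reduce the insulin-sensitivity gain from weight loss, and parent Aim 2 hypothesises that the gain is at least as large with higher protein. A change in HbA1c does not settle that question.

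The secondary point is that insulin sensitivity runs through the Purpose, parent Aims 2 and 3, the parent secondary outcomes and supplement Aim 3 without a stated measure. The analysis plans decline to adjust secondary and racial-difference outcomes for multiplicity. A measure left open until the data are in hand would therefore add a further unrecorded choice.

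**Working it through.** No power or effect calculation applies. The check sets the relevant places side by side.

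1. **How the plan uses HbA1c elsewhere.** The parent screening visit and the Inclusion Criteria use fasting plasma glucose or HbA1c to define prediabetes, and each may exceed its range somewhat if the other is within range. That is a glycaemic use.

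2. **Whether the plan treats the two constructs as one.** It does not appear to. Supplement Aim 2 has HbA1c as insulin resistance. Supplement Aim 3 lists insulin sensitivity separately and makes it depend on the return of in-person testing. If HbA1c were the intended insulin-sensitivity measure, Aim 3 would repeat Aim 2.

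3. **Whether an insulin-based measure is named.**

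| Place | Blood measures named | Insulin-based |
|---|---|---|
| Parent schedule | Metabolic panel | 0 |
| Supplement schedule | Metabolic panel | 0 |
| Privacy section, data list | Routine chemistries, HbA1c, GFR, fasting glucose | 0 |
| Privacy section, plasma description | HbA1c, GFR, fasting glucose | 0 |
| Privacy section, narrative | HbA1c, fasting glucose, GFR | 0 |
| Analysis plans, parent and supplement | No derived insulin variable | 0 |

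4. **What remains open.** The section on location of data and specimens says that plasma is kept at -80 degrees. The section on specimen transport says that specimens are analysed at a second institution, but not for what. The count of 0 therefore means that none is named, and does not show that none is planned.

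5. **Visits.** These are not the gap. The parent analysis plan sets baseline, 3 and 6 months, and the schedule footnotes set months 0 and 3 for the shortened study.

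6. **Specimen for HbA1c.** The supplement's Aim 2 list says whole blood, while the Privacy section lists HbA1c under plasma. Neither schedule gives HbA1c its own row. These entries need to be reconciled.

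7. **Extent.** Supplement Aim 2 has weight loss, physical function, insulin resistance (HbA1c), cognitive function and quality of life: 1 of 5 is mislabelled. Supplement size: 21 + 21 = 42.

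**The case against.** The best defence of the label is that HbA1c is printed beside it both times, so any reader can see what was measured. HbA1c is also a sensible stand-in while in-person testing was restricted, and the condition attached to supplement Aim 3 fits that account. Background and Significance further frames the open question partly as glucose handling, which HbA1c and fasting glucose do address. All of this supports keeping the measurement. None of it supports the name: reported as glycaemia, the same data would be correctly described.

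On the secondary point, a reader might infer that the trial has no means of measuring insulin sensitivity, or that the parent Aim 2 hypothesis cannot be tested. The documents do not support that. The stored plasma and the second laboratory leave room for an insulin assay or another index. The reference list also holds three entries (47 to 49) with no visible citation in the text, one of them on the oral glucose tolerance test. A description may have been cut, though that is only an inference.

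Nor should much be made of the single entry in the supplement's Aim 3 list. That list also omits the aim's own primary outcome, in-person SPPB, and the Aim 2 list omits quality of life. Both are abbreviated. Other outcomes, such as instrumental activities of daily living, also lack a named instrument, so insulin sensitivity is not unique in this respect.

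**Conclusion.** The labelling point holds. As written, supplement Aim 2 would present a glycaemia effect size as an insulin-resistance effect size. It concerns 1 of 5 secondary measures in a 42-person feasibility supplement and should be corrected.

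The secondary point holds only in this form: insulin sensitivity is a declared outcome, and no insulin-based analyte or index is named for it. It is largely missing detail. It touches one secondary outcome in parent Aim 2, the exploratory parent Aim 3 and the conditional supplement Aim 3.

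The SPPB primary outcome and the power statement, which concerns SPPB alone, are unaffected. No numerical bias can be computed from the documents. The verdict assumes that HbA1c is read in its ordinary sense as average glycaemia, which agrees with the plan's own eligibility use, and that the unnamed second-laboratory analyses are unknown rather than absent.

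**What to change.** **Label.** In both supplement Aim 2 statements, rename the outcome glycaemia (change in HbA1c) and draw no insulin-resistance conclusion from it. Add HbA1c and fasting glucose to both schedules at the existing visits: 0, 3 and 6 months, or 0 and 3 months for the shortened study. Reconcile whole blood with plasma for HbA1c. This is a text change. It needs no new data if, as the Privacy section says, both markers are already collected at all time points.

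**Insulin sensitivity.** Before any outcome is examined by arm, name the insulin-based measure that is planned, whether fasting insulin or another index, with its formula and visits, and say how oral glucose-lowering medication enters its analysis. If none is planned, consider whether one can be run on plasma already stored. If an assay is already planned, the cost is a short definition. A new assay would carry a laboratory cost, and its feasibility depends on which visits have stored plasma; the documents give neither.

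**Fallback.** Only if no such measure exists or can be run, limit conclusions from HbA1c and fasting glucose to glycaemia. Align the Purpose, parent Aims 2 and 3, the secondary outcome list, supplement Aim 3 and the benefit statement, and record this as a change of outcome. The cost is a narrower stated objective.
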